## Soft diet for temporomandibular joint pain

Good nutrition is very important for good health and well-being. If you are having jaw pain or difficulty chewing, you will need to modify the texture of your diet while maintaining an adequate nutrient (carbohydrate, protein, vitamins, minerals) and caloric intake.

Daily *minimum* food group requirements for adults include:

- 4 servings from the grains group
- 4 servings from the vegetable and fruit group
- 2 servings from the meat and protein group
- 2 servings from the milk group (4 servings for teenagers and young adults)

The following chart is designed to help you make healthy food choices.\*

Food Group	Allowed	Avoid
Grains (at least 4 servings/day) Bread or rolls	All plain, easy to chew.	Bread or rolls made with hard crust, seeds or nuts. Bagels.
Crackers	All plain, easy to chew.	Seeds or nuts.
Cereals	Cooked cereals: cream of wheat, cream of rice, Malt-O-Meal™, oatmeal. Dry cereals: corn, rice,	Granola or cereals that are advertised as “high fiber.”
Potatoes/Pasta/Rice	Mashed, baked (without skin), and creamed potatoes. Macaroni, pasta, rice, hominy.	Potato skins, wild rice, popcorn
Vegetables (at least 2 servings/day)	Cooked, tender vegetables; tomato and vegetable juice. Tender lettuce, tomatoes.	Raw vegetables.
Fruit (at least 2 servings/day)	All fruit juices. Raw fruits: soft, peeled such as banana, orange, peach, apricot or nectarine. Canned or cooked fruits without tough skins or membranes.	All other fresh fruit. Dried fruit.

*\*This material has been adapted from the Twin City District Dietetic Association manual.*

*Continued*

---

## APPENDIX D: HEALTH COACH PHONE PROTOCOL FOR PACT ARM

The Health Coach will assist patients who are participating in the PACT program by assessing, educating, and supporting patients in self-management to prevent chronic pain. The Coach will interact with patients through an on-line video conferencing, by phone, or through the Integrated Resource Information System (IRIS). Patients will be trained in reducing risk factors and enhancing protective factors for their pain condition. The Coach will be responsible for developing a health coaching relationship with them and assisting the patient through the process of care by actively working towards better health by providing support, encouragement, and education.

Health Coaching is relationship-centered, client-driven process designed to facilitate and empower a client to achieve self-determined goals related to health and overall well-being. While these goals may be informed by or suggested by others, such as an individual's physician or other health provider, the selection of the goal and exploration where one is relationship to the goal is up to the client. Individuals may be just beginning to consider a change, may be exploring aspects of preparing for a change, or may be ready to implement actual actions. In a safe and consistent space, clients can explore their thoughts, emotions, and actions, in a way that allows them to recognize the power of their own choices to impact their wellness.

Health Coaching is a methodology that differs from health education or counseling or therapy, though it can work well in combination with those other practices. Health Coaches assume that people have strong intrinsic resources and strengths, can access the self-motivation needed to function autonomously and competently, and are able to realize positive change within a safe and confidential alliance, where they are inspired, respected, and supported. By applying clearly defined knowledge and skills, they support individuals or groups in mobilizing their internal strengths and external resources to achieve sustainable changes in beliefs or behaviors. Health Coaching has the potential to help individuals, families, and groups achieve improved health and wellbeing.

### **Important Components of Health Coaching include;**

*Building a relationship.* Health coaching is relationship-centered, client-driven process designed to facilitate and empower a client to make changes that will help them achieve self-determined goals related to health and overall well-being. Health Coaching is a methodology that differs from health education, counseling or therapy, though it can work well in combination with those other practices. Health coaches facilitate the following;

*Setting goals.* While a person's goals may be informed by the condition, such as to reduce the pain, or suggested by others, such as a health professional or the on-line training such as to exercise, the health coach will help with selection of the goal and exploration where one is relationship to the goal is up to the client.

*Facilitating Change.* Individuals may be just beginning to consider a change, may be exploring aspects of preparing for a change, or may be ready to implement actual actions. In a safe, consistent, non-judgemental, and supportive space, clients can explore their thoughts, emotions, and actions, in a way that allows them to recognize the power of their own choices to impact their wellness.

*Empowering people.* Health coaches assume that people have strong intrinsic resources and strengths and can access the self-motivation and energy needed to accomplish their goals.

*Engaging responsibly.* Health coaches assume that people will function autonomously and competently, and are able to realize positive change within a safe and confidential alliance with the health coach. The coach relationship is one of inspiration, respect, and non-judgmental support.

*Achieving goals.* By applying clearly defined knowledge and skills, the health coach can support individuals or groups in mobilizing their internal strengths and external resources to achieve sustainable changes in thoughts, emotions, and behaviors. Health Coaching has the potential to help individuals, families, and groups achieve their goal of improved health and wellbeing.

*Coach Protocol.* Once the participant has enrolled in the PACT Study and been randomized to the PACT program, the phone coach will contact participant by telephone at varying intervals (see table 1). The role of the coach is to help the participant clarify their goals and identify strengths, resources, and barriers related to behavioral changes using motivational interviewing techniques. Coaches may also encourage completion of weekly educational module content and to inquire about the usefulness of the information, but that is a secondary focus.

## **RESPONSIBILITIES**

(include but are not limited to): The 4 basic responsibilities would be to 1) facilitate the patient's process of tapering the opioid medications and use of alternative medical management, 2) enhance understanding and compliance in self-management training for their condition address risk factors, and strengthen protective factors, 3) ensure patient is following up with health care provider for medical management, and 4) improve follow-up, outcomes, and quality of care. Thus, a health coach would also be working directly with the patients to help with the following;

- 1) Call the patient for an initial consult using video conferencing such as Skype, if available. An in-person meeting can be arranged also as needed
- 2) Understand the process of tapering opioids and replacing with alternative medical management interventions.
- 3) Understand addiction medicine and the patient-centered barriers and problems associated tapering from opioids and help address each one during the process.
- 4) Explain how the PACT program works and how to complete each training module and assessment instrument.
- 5) Answers questions that many patients still have about their problem and how it will be addressed with treatment plan.
- 6) Complete the assessment of risk and protective factors through the PACT program
- 7) Call the patient biweekly by video-conferencing to reinforce compliance and understanding and ensure follow-up with each team member.
- 8) Facilitate review of on-line modules for self-management training to reinforce the doctor's information.
- 9) Explain health education materials to patient, when questions arise
- 10) Provides the patient with a pain diary to document progress with changing pain, functional status, identify triggers, risk factors, protective factors and barriers to success. They will work with the team to improve outcomes.

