## **KNOWLEDGE AND SKILL**

Bachelor's degree or higher in health promotion, health education, nursing, athletic training, nutrition, psychology, social work, or other health related field or counseling and training certificate in health coaching. Knowledge of specific disease and lifestyle related topics such as pain management, smoking cessation, weight management, nutrition, pre-post natal care, stress reduction and chronic conditions and certification from an accredited professional health coach training program preferred.

**PROTOCOL:** Once the participant has enrolled in the PACT Study and been randomized to the PACT program, the phone coach will contact participant by telephone at varying intervals (see table 1). The role of the coach is to help the participant clarify their goals and identify strengths, resources, and barriers related to behavioral changes using motivational interviewing techniques. Coaches may also encourage completion of weekly educational module content and to inquire about the usefulness of the information, but that is a secondary focus.

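### Appendix D's Responsibilities list gives coaches an opioid-tapering duty that no other coach text supports (minor, but wrong as written)

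*Protocol*

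**What the plan says.** Section 5.8 refers the reader to Appendix D for the coach phone protocol. Under Responsibilities, that appendix names four basic duties and then ten numbered tasks. Three of these items concern opioids:

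- Responsibility 1 is to facilitate the "process of tapering the opioid medications and use of alternative medical management".
- Task 2 reads "Understand the process of tapering opioids and replacing with alternative medical management interventions".
- Task 3 reads "Understand addiction medicine and the patient-centered barriers and problems associated tapering from opioids and help address each one during the process".

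Responsibility 3 in the same list asks the coach to "ensure patient is following up with health care provider for medical management".

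The role statement appears twice in Appendix D, just before the list and again shortly after it: "The role of the coach is to help the participant clarify their goals and identify strengths, resources, and barriers related to behavioral changes". The Knowledge and Skill paragraph that follows the list asks for "Knowledge of specific disease and lifestyle related topics such as pain management, smoking cessation, weight management, nutrition" and some further topics.

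**The concern.** Helping a patient come off opioids is a medication-related task. Here it is put first among the duties of non-prescribing coaches, in a behavioral study that the protocol describes as minimal risk. If it were meant as part of PACT, one would expect to see it in the intervention description, the coaches' training, the fidelity check and the call content, with a prescriber named. If it were not meant, it should not stand in the document to which Section 5.8 sends coaches.

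Two things are at stake. One is how the intervention is defined, since this pilot tests methods for a multi-site trial and an uncorrected coach protocol could be passed on to more sites. The other is the safety of any PACT participant who takes opioids and whose coach works from the list.

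**Working it through.** The protocol gives no figure to reproduce here. The check sets the texts side by side, first for the duty and then for who could be exposed to it.

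**Where the duty appears**

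- Appendix D, Responsibilities: responsibility 1, task 2 and task 3, so three items.
- Sections 5.7.1 and 5.8 (intervention): coaches support understanding, adherence, goals and motivation. No tapering.
- Section 5.9 (training): the protocol, the PACT manual, TMD care, an examined online chronic-pain course, going through PACT themselves, and discussion sessions. No tapering is named.
- Sections 5.8 and 5.9 (fidelity): log review of contacts and of the coaching model, and five points on relationship, goals, strengths and barriers, module completion and usefulness. No tapering.
- Appendix D, role statement, duties for the initial, program and final calls, and Table 1: goals, resources, barriers and progress through the modules. No tapering.
- Appendix B (lessons): Lesson 1 has a session reviewing pain treatments, opioids included, and Lesson 3 has one on substance use. Both are online education; neither is a tapering program or a coach task.
- SAP: nothing on this subject.

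The duty therefore stands only in the Responsibilities list. The consent form was not in the text available for this check.

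**Who could be exposed**

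Text that narrows the pool:

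- Section 4 asks all participants to restrict other medication to NSAIDs.
- Section 5.2 excludes people whose major disc disorder requires opioids, and anyone treated for a mental health disorder or substance abuse in the preceding six months.
- Section 6.1 gives psychiatric disorder and systemic pain disorder as examples of screening exclusions.

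Text that leaves it open:

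- The NSAID limit is a request and not an eligibility criterion.
- Section 5.11 allows other TMD treatments, medication among them, without naming or excluding opioids.
- The phone screen in Appendix E has no opioid question. Item 17 asks about planned surgery but not about the opioid part of the Section 5.2 criterion.

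The documents do not say how many PACT participants take opioids. Section 11.2 puts 40 people in that arm, so the range is 0 to 40. The upper end is only the arm size, not an estimate, and the exclusions point toward the lower end.

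**What a coach following the list would have**

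- Provider contact: responsibility 3 requires it, but neither it nor any other item assigns a prescriber to the taper.
- Supervision: investigators meet the coaches monthly to review their discussions with patients (Section 5.9).
- Event capture: adverse events are to be recorded whatever their cause (Section 8.1.2).
- Training: none stated to cover tapering.

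**The case against.** The best defense is that the list reads like a generic job description. It is worded conditionally and is followed by degree requirements and by topics, such as care around childbirth, that have nothing to do with TMD. The study-specific instructions are given more than once, are consistent, and never mention opioids. A coach who follows the calls as laid out would not raise tapering. The duty is also one of support and does not extend to setting doses, and the same sentence calls for provider follow-up. This stands, and it is why the point is minor. It does not make the list correct: the items sit inside the appendix that Section 5.8 designates as the coach protocol, and nothing marks them as inapplicable.

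Three stronger readings are tempting, and the documents do not support them.

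- A reader might infer that coaches would manage opioid withdrawal without oversight. Monthly supervision, the study coordinator's frequent contact with coaches (Section 8), provider follow-up and adverse-event recording all exist.
- A reader might infer that coaches are untrained in tapering. The contents of the PACT manual and of the chronic-pain course are not in the documents, and the Knowledge and Skill topics are given as examples only. One can say that no such training is stated, not that there is none.
- A reader might infer that a sizeable share of the PACT arm is at risk. The Section 4 request and the exclusions in Sections 5.2 and 6.1 argue against that.

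**Conclusion.** The inconsistency is real and the text is wrong as written. Three items in Appendix D give coaches a tapering duty that the rest of the protocol neither describes nor equips them for. Severity is minor: few participants are likely to be affected, possibly none, and harm would need both an enrolled opioid user and a coach who acted on the list instead of the call content.

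The conclusion rests on two judgments. The first is that the items were carried over from another program; this is inferred from their isolation and their poor fit with the population, since the documents do not say where the list came from. The second is that Section 4, Section 5.2 and Section 6.1 are applied as written, which keeps exposure low without excluding it. Nothing here touches the feasibility endpoints, the sample size of 80 or the descriptive analysis in Section 11.4 and the SAP.

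**What to change.** In Appendix D, Responsibilities:

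- Delete responsibility 1 and tasks 2 and 3.
- Change the stated number of basic responsibilities from four to three (4 − 1 = 3) and renumber the remaining eight tasks (10 − 2 = 8).
- Add one sentence telling coaches to refer any opioid question to the treating provider. The present responsibility 3 stays and supports that referral.

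The cost is a short amendment, which needs IRB approval under Section 14.2, and a note to the three coaches.

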## **KNOWLEDGE AND SKILL**

Bachelor's degree or higher in health promotion, health education, nursing, athletic training, nutrition, psychology, social work, or other health related field or counseling and training certificate in health coaching. Knowledge of specific disease and lifestyle related topics such as pain management, smoking cessation, weight management, nutrition, pre-post natal care, stress reduction and chronic conditions and certification from an accredited professional health coach training program preferred.

**PROTOCOL:** Once the participant has enrolled in the PACT Study and been randomized to the PACT program, the phone coach will contact participant by telephone at varying intervals (see table 1). The role of the coach is to help the participant clarify their goals and identify strengths, resources, and barriers related to behavioral changes using motivational interviewing techniques. Coaches may also encourage completion of weekly educational module content and to inquire about the usefulness of the information, but that is a secondary focus.

### Contact, duration, and frequency

- Minimum phone contact: Initial call, touch base call, and final call
- Maximum phone contact: Two times per week for three months
- The intention is for an initial call of 30-60 min (as needed) followed by 30 minute follow-ups
- Documentation will occur at all calls to collect time and focus of the session and self-identified goals (yes?)

### During the initial phone call, the phone coach will be responsible for:

- 1) Explanation of coaching – how it works, expectations
- 2) Set ground rules and determine interaction frequency
  - At minimum the participant needs to have an initial call, a touch base call, and a final call
- 3) Determination of participant needs, goals, and barriers. What do they want to work on?
  - Example questions that may be asked: What is important? What strengths have led to success? Types of barriers to success? What steps have you taken to achieve your goal? Pattern of thoughts getting in your way?
- 4) Foster motivation and help participant to prioritize and address goals and barriers, applying collaborative communication techniques supporting the client's power to direct their own agenda

During program calls, the phone coaches' responsibility will be to:

- 1) Touch base on where the participant is at with their goals
- 2) Help participant clarify goals and identify and address resources and barriers
- 3) Check-in about online training program progression and impact
- 4) Base discussion on current happenings in participant's life and client's agenda in the moment

During the final phone call, the phone coach will be responsible for:

- 1) Final determination of where the participant is at in achieving or moving toward their goal(s)
- 2) Mention that the participant may be eligible, based on their insurance coverage, to have access to coaching services. If this is something of interest, direct them to member services at their health plan

Table 1: Frequency of Phone Calls for Health Coaches		
Time Period	Frequency of Contact	Content
Study Month 1	At most 2 times/week	1) Touch base on where the participant is at with their goal(s) 2) Help participant clarify goals and identify and address resources and barriers 3) Check-in about online training program progression and impact 4) Base discussion on current happenings in participant's life and client's agenda in the moment
Study Month 2	Same as above	Same as the above
Study Month 3	Last call	1) Final determination of where the participant is at in achieving their goal(s) 2) Mention that the participant may be eligible, based on their insurance coverage, to have access to coaching services. If this is something of interest, direct them to member services at their health plan

**Forms and Supplies Needed**

- Participant's home phone number and email address.
- PACT program website access
- Weekly Log

Chart on Preventing Chronic Pain in the Seven Realms			
	Triggers pain flares	Risk Factors to avoid	Protective actions to follow
B Body	Poor posture Tensing, strain to muscle Over-vigorous exercise, strenuous labor Acute injury Menstrual cycle, thyroid, hormonal changes	Tense and poor postures Repetitive muscle strain Poor conditioning Weak muscles Illness, obesity, hypermobile joints	Balanced relaxed posture during day Conditioning exercises Strengthening exercise Avoid physical risks to avoid injury
L Lifestyle	Diet triggers* (see below) Dehydration Poor sleep/ oversleeping Chemical, caffeine, tobacco products Stress-too busy, shift work hours	Poor diet and sleep Inactivity/ prolonged sitting Hurrying, feeling rushed Extreme sports/activity Chemical and tobacco use Irregular lifestyle, shift work	Healthy diet daily(see handout) Diet supplements Staying active all day Follow good sleep routine Pace through-out the day Take actions to be safe daily
E Emotion	Anxious/ crisis situation Prolonged depression or sadness Prolonged anger	Anger Anxiety Nervousness Sadness Depression	Be creative: cooking, art, music, writing Deep breathing exercise Practice relaxation to calm muscles, nerves Practice positive psychology: Identify blessings Identify, discover, express your emotions
S Society	Stress- family Stress- people at work Stress- new/changing job Stress- loss of job Stress- financial PTSD	Self-centered and ego-centric Conflict and abuse Lack of social support Feeling lonely and isolated Secondary gain Intolerant/ Unforgiving	Cultivate positive relationships Help others daily Be courteous and respectful Provide social support to those around you Create win-win in resolving conflicts

S Spirit
	
Feeling lost                  Burned-out                  Hate and dislikes in life                  Self-abuse
	
Stress and burnout                  Hate and loathing                  Low self esteem                  Lost and meaningless life                  Disbelief/ cynicism/ doubt                  Hopelessness and pessimism
	
Mindfulness meditation and prayer                  Find meaning in life                  Maintain love and passion in life                  Explore dreams, hopes, and aspirations


M Mind
	
Stress- confusion, being ill-prepared                  Stress- dishonest, cheating                  Stress- fail to meet expectations                  Stress- out of control situations                  Stress- poor resilience
	
Ignorance of whole problem                  Low resilience and coping                  Low self-efficacy/ control                  Deny responsibility                  Poor compliance                  Unrealistic expectations
	
Learn about condition/risk/ protective factors                  humor, balance, flexible, tough, centered                  Self-motivated, growth, responsible write positive affirmations                  Practice adapt to new situations                  Learn realistic outcomes

E Environment
	
Air pollution/ allergens                  Weather changes                  Noise                  Vibration                  High altitudes and environmental triggers
	
Infection prone and unclean                  Chaotic environment                  Dangerous surroundings                  Accident prone                  Negligent
	
Clean and organize the home                  Reduce air pollution, allergens, vibrations                  Follow food safety plan create safe home and work environment                  Reduce risks and drive defensively

